# 2. TRIAL OBJECTIVES AND ENDPOINTS

# 2.1 MAIN OBJECTIVES, PRIMARY AND SECONDARY ENDPOINTS

Final endpoints for Part 2 will be supported by study results available at the time of Part 1 primary analysis

# 2.1.1 Main objectives

Section 2.1.3 and Section 2.2.2).

Study 1368-0098 consists of 2 parts: dose finding Phase IIb (Part 1), designed to find the optimal dose in patients with moderate to severe HS for Phase III development; confirmatory Phase III (Part 2), designed to assess the efficacy and safety of spesolimab in patients with moderate to severe HS. Patients recruited in Part 1 cannot participate in Part 2.

## Part 1 (Phase IIb)

The dose finding phase (Part 1) will characterise the dose-response curve and exposure-response relationship and will support identifying the dose of spesolimab providing the most adequate benefit/risk to patients with moderate to severe HS by assessing 3 dosing regimens (for detailed dosing regimens, please see Section 3.1 and Section 4.1.4) and placebo.

The primary objective of dose finding phase are as follows (for summary measure of treatment effect, please see Section 2.1.2):

(1) to demonstrate a non-flat dose response curve, evaluate the quantitative treatment effect size, and evaluate the dose-response relationship based on the primary endpoint of percent change from baseline in dT count at

(2) to determine an optimal dose candidate for Part 2 by incorporating information of available safety and of efficacy based on the primary endpoint of percent change from baseline in dT count at

available safety and of efficacy based on the primary endpoint of percent change from baseline in dT count at

The secondary objectives are as follows:

(1) to demonstrate non-flat dose response curve based on selected secondary and further efficacy endpoints at

(2) to evaluate the quantitative treatment effect size of percent change from baseline in dT count at

and absolute change from baseline in International Hidradenitis

Suppurativa Severity Score System (IHS4) value at

(3) to evaluate the sustainability of spesolimab efficacy up to

(4) to assess safety of spesolimab.

The secondary objectives will be served by selected secondary and further efficacy endpoints, as well as safety endpoints (for list of secondary and further endpoints, please see

The primary and secondary analyses will be based on Full analysis set (FAS), defined as trial participants randomised in Part 1 and having received at least 1 dose of study drug. Treatment comparisons will be performed regardless of treatment adherence.

Boehringer Ingelheim BI Trial No.: 1368-0098

c40061625-02

**Clinical Trial Protocol** 

Page 41 of 177

Proprietary confidential information © 2023 Boehringer Ingelheim International GmbH or one or more of its affiliated companies

Part 2 (Phase III)	
Because of the use of modelling,	
in Part1.	
The confirmatory phase aims to provide substantial evidence of the efficacy, safety, and tolerability of spesolimab in comparison to placebo in trial participants with moderate to severe HS.	

Part 2 will not be conducted if the analysis of Part 1 (Phase IIb) at data cut-off does not conclude to potential of spesolimab for demonstrated clinical benefit versus placebo in terms of effect size and sustainability. The dose for Part 2 (Phase III) will be based on all available data at the time of primary analysis when last trial participant complete Visit 10

The primary objective of the confirmatory phase (Part 2) is to demonstrate superiority of one dosing regimen of spesolimab (identified on the basis of Phase IIb data analysis) against placebo in the

The secondary objectives are as follows:

- (1) to demonstrate superiority of spesolimab against placebo for the key secondary endpoints (please see Section 2.1.3).
- (2) to assess safety of spesolimab.

The primary and secondary analyses will be based on the TS, defined as trial participants randomised in Part 2 and having received at least 1 dose of study drug. Treatment comparisons will be performed regardless of treatment adherence.

# 2.1.2 Primary endpoints

# Part 1 (Phase IIb)

Percent change from baseline in dT count at

# Part 2 (Phase III)

Percent change from baseline in dT count at

# 2.1.3 Secondary endpoints

## Part 1 (Phase IIb)

## **Efficacy**

# Secondary endpoint

- Percent change from baseline in dT count at
- Absolute change from baseline in IHS4 value at
- Absolute change from baseline in IHS4 value at

Page 42 of 177

Proprietary confidential information © 2023 Boehringer Ingelheim International GmbH or one or more of its affiliated companies

#### Safety

Occurrence of treatment emergent adverse events (TEAEs)

#### Part 2 (Phase III)

# **Efficacy**

Key secondary endpoints

The following key secondary endpoints will be considered. These may be amended according to Part 1 results:

- Absolute change from baseline in IHS4 value at
- Absolute change from baseline in Hidradenitis Suppurativa Area Severity Index (HASI) score at
- Achievement of Hidradenitis Suppurativa Clinical Response (HiSCR50) at Week 16: HiSCR50 is defined as at least a 50% reduction in the total abscess and inflammatory nodule (AN) count with no increase in abscess count and no increase in dT count relative to baseline.
- Percent change from baseline in abscess count at
- Achievement of at least a 50% reduction in dT count at relative to baseline.
- Achievement of at least a 50% reduction in abscess and dT (AdT) count at relative to baseline
- Achievement of at least a 50% reduction in ANdT count at relative to baseline.
- Achievement of at least 30% reduction from baseline in Numerical rating Scale (NRS30) in Patient's Global Assessment of HS pain at

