# Part 1 (Phase IIb)

# **Efficacy**

Lesion counts clinical endpoints

- Percent change from baseline in dT count at each scheduled assessment.
- Achievement of at least 50% reduction from baseline in dT count at each scheduled assessment.
- Occurrence of complete elimination of dT at each scheduled assessment.
- Time to first occurrence of complete elimination of dT during the treatment period.
- Percent change from baseline in abscess count at each scheduled assessment.
- Achievement of at least 50% reduction from baseline in abscess count at each scheduled assessment.
- Occurrence of complete elimination of abscess at each scheduled assessment.
- Percent change from baseline in total AdT count at each scheduled assessment.
- Achievement of at least 50% reduction from baseline in AdT count at each scheduled assessment.
- Percent change from baseline in inflammatory nodule (N) count at each scheduled assessment.
- Percent change from baseline in total ANdT count at each scheduled assessment.
- Achievement of at least 50% reduction from baseline in ANdT count at each scheduled assessment.

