#### 3.3.2 Inclusion criteria

#### Part 1 (Phase IIb)

- 1. Of full age of consent (according to local legislation, at least  $\geq$  18 years) at screening.
- 2. Signed and dated written informed consent in accordance with ICH-GCP and local legislation prior to admission to the trial.
- 3. Moderate to severe HS, based on IHS4 criteria, at least 6 months prior to and including Baseline visit, as determined by the investigator through participant interview and/or review of the medical history (if IHS4 scoring is not available for the period before screening, equivalent scoring based on scoring systems as HS-PGA or Hurley are acceptable on the basis of documented investigator assessment)
- 4. HS lesions anatomic areas
- 5. Biologic naive or
- 6. For biologic naïve, inadequate response to an adequate course of appropriate oral antibiotics for treatment of HS in the last 1 year prior to the Baseline visit, as per investigator discretion. All participants must have previous exposure to antibiotics for HS.
- 7. Total AN count of at Baseline visit.
- 8. Total dT count Baseline visit
- 9. Women of childbearing potential (WOCBP) must be ready and able to use highly effective methods of birth control per ICH M3 (R2) that result in a low failure rate of less than 1% per year when used consistently and correctly, for the duration of the trial and after last administration. A list of contraception methods meeting these criteria and instructions on the duration of their use is provided in the participant information and in Section 4.2.2.3

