#### Part 2 (Phase III)

Except for potential criteria, which will be confirmed after primary analysis of Phase IIb results, the same inclusion criteria as Part 1 (Phase IIb) will need to be met.

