#### Part 2 (Phase III)

### Efficacy endpoints

In the primary analysis of primary and continuous key secondary endpoints, missing data will not be imputed except for death (unexpected), where a poor outcome will be assigned. The mixed effect model will handle missing data based on a likelihood method under the 'missing at random assumption'.

Sensitivity analyses for handling missing primary and continuous key secondary endpoints data will be specified in the TSAP.

In the primary analysis of binary key secondary endpoints, a No Response Imputation (NRI) approach will be applied to the missing visits up to that is, imputing as a failure to achieve a response in the visits with missing endpoint score, however:

- If there are available data at the visits both before and after the visit with a missing outcome, then impute as a success only if both the preceding and the following measurement indicate success.
- Otherwise, impute as a failure to achieve a response (i.e. no response imputation)

NRI is a conservative imputation scheme because it assumes that missing data due to any reason is related to treatment failure.

Sensitivity analyses for handling missing binary key secondary endpoints data will be specified in the TSAP.

Full details on the handling of missing data will be specified in the TSAP prior to unblinding.

Page 115 of 177

Proprietary confidential information © 2023 Boehringer Ingelheim International GmbH or one or more of its affiliated companies

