# 10.3 HIDRADENITIS SUPPURATIVA CLINICAL RESPONSE (HISCR)

Defined as at least a 50% reduction from baseline in the total abscess and inflammatory nodule count, with no increase in the abscess or draining fistula count.

		Patient 1			Patient 2	:
	Baseline	Week 12	HISCR Criteria	Baseline	Week 12	HiSCR Criteria
Total abscess and inflammatory nodule (AN) count	20	10	1	20	10	1
Abscesses	5	5	1	5	8	×
Inflammatory nodules	15	5	1	15	2	1
Draining fistulas	4	4	1	4	2	1

[figure not shown]
*Fig. Source:* HUMIRA Hidradenitis Suppurativa Clinical Response (HiSCR) Data (humiradermpro.com)

Page 131 of 177

Proprietary confidential information © 2023 Boehringer Ingelheim International GmbH or one or more of its affiliated companies

[figure not shown]

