4. CHANGES IN THE PLANNED ANALYSIS OF THE STUDY

All analyses stated in the CTP (latest version) will be performed as planned with the following adaptations.

The below further efficacy endpoints have been updated:

- Achievement of HiSCR50 at each scheduled assessment.
 HiSCR50 is defined as at least a 50% reduction from baseline in the total abscess and inflammatory nodule count, with no increase in the abscess or draining fistula count.
- Absolute change from baseline in Patient Global Impression of Change (PGI-C) score over time.

This endpoint will be updated to:

Patient Global Impression of Change (PGI-C) score at each scheduled assessment over time.

• Absolute change from baseline in Patient Global Impression of Severity (PGI-S) score over time.

This endpoint will be updated to:

Date: 07-08-2024, Version 1.0

Patient Global Impression of Severity (PGI-S) score at each scheduled assessment over time.

The below further efficacy endpoints, which were not specified in the CTP version 2.0, have been added:

- Achievement of HiSCR75 at each scheduled assessment.
 HiSCR75 is defined as at least a 75% reduction from baseline in the total abscess and inflammatory nodule count, with no increase in the abscess or draining fistula count.
- Achievement of HiSCR90 at each scheduled assessment.
 HiSCR90 is defined as at least a 90% reduction from baseline in the total abscess and inflammatory nodule count, with no increase in the abscess or draining fistula count.
- Achievement of mHiSCR at each scheduled assessment: mHiSCR is defined as at least a 50% reduction in total ANdT count relative to baseline. and at least 50% reduction in total dT count relative to baseline.
- Achievement of mHiSCR-AdT at each scheduled assessment: mHiSCR-AdT is defined as at least a 50% reduction in the total AdT count with no increase in inflammatory nodule count, no increase in abscess count, and no increase in dT count relative to baseline.
- Achievement of mHiSCR-AdT(2) at each scheduled assessment: mHiSCR-AdT (2) is defined as at least 50% reduction in the total ANdT count relative to baseline and at least 50% reduction in total AdT count relative to baseline.

Boehringer Ingelheim TRIAL STATISTICAL ANALYSIS PLAN 1368-0098

Date: 07-08-2024, Version 1.0

Page 10 of 64

c43421787-01

- Achievement of 2 points reduction in Physician's Global Assessment (PGA) score from baseline at each scheduled assessment (only for patients with a PGA \geq 2 at baseline).

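### Does percent change in abscess count need replacing because it has no value when a participant starts with no abscesses?

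*Protocol*

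**What the plan says.** Protocol Section 2.1.3 names "Percent change from baseline in abscess count at" a redacted visit as a candidate Part 2 key secondary endpoint, and says of the whole list: "These may be amended according to Part 1 results". Section 2.2.2 gives the visit-by-visit form for both parts, "Percent change from baseline in abscess count at each scheduled assessment", together with two responder endpoints: a halving of the abscess count and its complete elimination.

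The lesion-count entry criteria in Section 3.3.2 concern the combined count ("Total AN count of at Baseline visit", threshold redacted) and the draining tunnel count. For Part 2, apart from items still to be confirmed, "the same inclusion criteria as Part 1 (Phase IIb) will need to be met". Appendix 10.3 shows that the combined count is a sum: its row "Total abscess and inflammatory nodule (AN) count" reads 20, made up of 5 abscesses and 15 nodules.

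On missing data in Part 2, Section 7.3 says: "In the primary analysis of primary and continuous key secondary endpoints, missing data will not be imputed except for death (unexpected"). It leaves full details to the statistical analysis plan, to be fixed before unblinding. The SAP covers Part 1 only. Its Section 4 restricts one added endpoint by baseline status, a 2-point drop in "score from baseline at each scheduled assessment (only for patients with a PGA" of at least 2. No similar restriction can be read for abscesses.

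**The concern.** A participant with nodules and draining tunnels but no abscess can meet a threshold on the combined count, wherever that threshold lies. For that person percent change has no value, and with no imputation the record drops out of a repeated-measures model. The abscess result would then describe only participants with at least one baseline abscess, not everyone randomised and dosed. Small denominators add noise: at a baseline of 1, one extra abscess is +100%.

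The responder endpoints raise a related question. Someone with no abscess at baseline and none later could be counted as a success, counted as a failure or left out. The apparent remedy is to analyse absolute change, adjusted for baseline, in everyone. The SAP already has model code of that form for IHS4 in Section 7.5.2.

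**Working it through.** The plan has no figure to reproduce. Part 2 sample size, effect and power are redacted, and no mean, SD or zero share is given for abscesses. Every abscess input below is an assumption.

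**1. The gap.** Percent change = 100 × (Y − B)/B, with B the baseline count and Y the follow-up count. It is undefined at B = 0. B is fixed before treatment, so leaving out B = 0 removes comparable participants from both arms.

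**2. Cost of a smaller analysed group.** Borrow the tunnel figures: a 30-point difference (Protocol 7.2.3, Part 1), SD 50 points and one-sided 2.5% (Protocol 7.5, Part 2). For 90% power, n = 2 × (1.960 + 1.282)² × (50/30)² = 58.4, so 59 per arm.

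| Assumed share with B = 0 | Left per arm | Power |
|---|---|---|
| 0% | 59 | 0.90 |
| 10% | 53.1 | 0.87 |
| 30% | 41.3 | 0.78 |
| 50% | 29.5 | 0.64 |

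This is the cost of a smaller n. It does not show that another endpoint recovers the loss, because participants at zero can only stay level or worsen.

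**3. Does absolute change in everyone do better?** Take baseline counts as Gamma-Poisson with mean m and shape k, so the zero share is (k/(k + m))^k. Use 100 per arm and a linear model with treatment and baseline. Participants at zero have a control follow-up mean of 0.1. Two follow-up models:

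- *Count model:* follow-up is drawn afresh around the person's own rate (× 0.9, and × 0.65 on active).
- *Percent model:* follow-up is set by a percent change averaging −10% on placebo and −40% on active, SD 50 points, rounded and floored at zero. These are the tunnel assumptions of Protocol 7.2.3 and 7.5.

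Each cell gives power for percent change in B > 0, then for absolute change in all:

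| m, k | Zero share | Count model | Percent model |
|---|---|---|---|
| 1, 1 | 0.50 | 0.31, 0.40 | 0.76, 0.68 |
| 2, 1 | 0.33 | 0.47, 0.60 | 0.89, 0.78 |
| 3, 1 | 0.25 | 0.59, 0.75 | 0.93, 0.80 |
| 3, 5 | 0.10 | 0.72, 0.87 | 0.95, 0.92 |

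The order reverses. In the count model the ratio is very noisy at low baselines. In the percent model its spread is about the same at every baseline, and high counts dominate the absolute scale. Across 66 count-model settings absolute change led by 2 to 25 points. Across 28 percent-model settings the result ran from 2 points against percent change to 19 points for it.

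**4. How much of the count-model gap comes from the zeros?** At m = 2, k = 1, absolute change restricted to B > 0 has power 0.59. The metric therefore accounts for 0.59 − 0.47 = 12 points and dropping the zeros for 0.60 − 0.59 = 1 point. If participants at zero instead go on developing abscesses at their own rate, the three powers are 0.48, 0.61 and 0.67, so 13 and 6 points. Most of the gap is a preference between scales.

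**5. Responder coding.** Largest case, m = 1, k = 1, half at zero, 56% control response among the rest. Zeros as failures: 0.50 × 56% = 28%. Zeros excluded: 56%. Zero staying at zero as success: 28% + 0.50 × e^(−0.1) = 28% + 45% = 73%. The level moves a great deal, but any one rule applies to both arms alike.

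**The case for a change.** The best case for a change starts from a fact that redaction cannot remove. Any rule for percent change must either leave out participants at zero or give them an arbitrary value, and neither cures small denominators. The sponsor has seen the issue elsewhere: Protocol 3.2 says that an endpoint whose name is redacted, apparently the tunnel primary, cannot be evaluated in patients without lesions at baseline. There is a tunnel entry criterion and a baseline restriction for the PGA endpoint, but nothing readable for abscesses. Amendments for Part 2 are planned anyway, and the IHS4 model could be reused at little cost.

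The undefined value and the absence of a readable rule stand. So does the point that responder rates need a stated denominator to be interpreted.

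The step to a different endpoint does not. Small denominators are a property of percent change in general, including the draining tunnel primary the sponsor chose. Absolute change weights participants with high counts more heavily, and a normal-errors model for skewed counts has difficulties of its own. Absence of a readable rule is also weak evidence: the Part 2 text of Protocol 7.2.4 is not visible, and much of the SAP on further endpoints and derivations is missing from the public copy.

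**Conclusion.** No change to the plan follows. What remains is a detail that an analyst would fill sensibly: analyse participants with at least one baseline abscess and report how many were left out per arm. The SAP's PGA endpoint already has this form, and the default of dropping undefined values leads to the same analysed group without bias between arms. The Part 2 analysis plan, still to come, is the natural place to state it.

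The stakes are small. The percent-change endpoint is provisional in Part 2 and exploratory in Part 1. The two abscess responder endpoints are not on the Part 2 key secondary list. Abscesses in all participants still count in HiSCR50, IHS4, AdT and ANdT.

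Replacing percent change by absolute change is a trade-off. In the settings tabulated above, the difference ranges from 16 points of power for absolute change (0.75 − 0.59) to 13 points against it (0.80 − 0.93), depending only on the assumed follow-up model and baseline distribution. This rests on assumed abscess counts and on tunnel assumptions borrowed for abscesses. The documents allow neither to be checked.

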#### **Safety**

Occurrence of TEAEs.

#### 2.2 FURTHER OBJECTIVES AND FURTHER ENDPOINTS

## 2.2.1 Further objectives

Further objectives are to evaluate further measures of efficacy including effect size up to the pharmacokinetics (PK), the immunogenicity (anti-drug antibody [ADA] and neutralizing antibody [NAb]) of spesolimab, and to explore biomarkers related to changes in HS and IL36 pathway after treatment (assessment of gene expression levels in skin biopsies and whole blood, evaluation of serum proteomics and imaging markers acquired by ultrasound [US]).

## 2.2.2 Further endpoints

For further endpoints, time-point defined as "at each scheduled assessment" refers to scheduled assessment for the related outcome as per Flowchart. More details and additional further endpoints may be defined in the TSAP.

Page 43 of 177

Proprietary confidential information © 2023 Boehringer Ingelheim International GmbH or one or more of its affiliated companies

# Part 1 (Phase IIb)

# **Efficacy**

Lesion counts clinical endpoints

- Percent change from baseline in dT count at each scheduled assessment.
- Achievement of at least 50% reduction from baseline in dT count at each scheduled assessment.
- Occurrence of complete elimination of dT at each scheduled assessment.
- Time to first occurrence of complete elimination of dT during the treatment period.
- Percent change from baseline in abscess count at each scheduled assessment.
- Achievement of at least 50% reduction from baseline in abscess count at each scheduled assessment.
- Occurrence of complete elimination of abscess at each scheduled assessment.
- Percent change from baseline in total AdT count at each scheduled assessment.
- Achievement of at least 50% reduction from baseline in AdT count at each scheduled assessment.
- Percent change from baseline in inflammatory nodule (N) count at each scheduled assessment.
- Percent change from baseline in total ANdT count at each scheduled assessment.
- Achievement of at least 50% reduction from baseline in ANdT count at each scheduled assessment.

# Response-, score-, and flare-related clinical endpoints

- Achievement of HiSCR50 at each scheduled assessment.
- Absolute change from baseline in IHS4 value at each scheduled assessment.
- Achievement of IHS4-55 response (defined as at least 55% reduction from baseline) at each scheduled assessment.
- Absolute change from baseline in HASI score at each scheduled assessment.
- Achievement of Physician's Global Assessment (PGA) score of 0 or 1 at each scheduled assessment.
- Occurrence of at least one HS flare at each scheduled assessment: defined as at least 25 % increase in AN count with a minimum increase of 2 relative to baseline.
- Time to first occurrence of HS flare during the treatment period.

